C-SSRS	Columbia Suicide Severity Rating Scale
CV	coefficient of variation
DKEFS	Delis-Kaplan Executive Function System
DSST	Digit Symbol Substitution Test
ECG	electrocardiogram
EMACC	Early AD/ MCI Alzheimer's Cognitive Composite
E _{max}	Maximum response
EOS	End of study
EOT	End of treatment
ET	Early termination
FAQ	Functional Activities Questionnaire
FAS	Full Analysis Set
eCOG	Everyday Cognition
ICH	International Conference on Harmonisation
INR	Prothrombin Intl. Normalized Ratio
IRT	interactive response technology
iADRS	The Integrated Alzheimer's Disease Rating Scale
LS	Lease Square Mean
ISLR	International Shopping List Test Delayed Recall
ISLT	International Shopping List Test Immediate Recall
LLOQ	lower limit of quantification
LTE	long-term extension
LP	Lumbar puncture
MA	macrohemorrhages
MCI	mild cognitive impairment

CONFIDENTIAL

The information contained herein may not be used, disclosed, or published without the written consent of Biogen MA Inc.

MedDRA	Medical Dictionary for Regulatory Activities
mH	microhemorrhages
MMRM	mixed-model repeated measures
MMSE	Mini-Mental State Examination ³
MRI	magnetic resonance imaging
NPI-10	Neuropsychiatric Inventory-10
PC	Placebo control
PCP	Placebo control period
PCS	potentially clinically significant
PD	Pharmacodynamics(s)
PET	positron emission tomography
PLS	Partial least squares
PK	pharmacokinetic(s)
PT	Preferred term
PT	Prothrombin Time
QoL-AD	Quality of Life for Alzheimer's Disease
QTcF	Corrected QT interval by Fredericia
ROI	region of interest
RUD-Lite	Resource Utilization in Dementia – Lite Version
SAE	serious adverse event
SAP	statistical analysis plan
SD	standard deviation
SOC	System organ class
SS	superficial siderosis
SUVr	standard uptake value ratio
TEAE	treatment-emergent adverse event
TIV	Total Intracranial Volume
Trails A	Trail Making Test, Part A
ULN	upper limit of normal
VE	vasogenic edema
WHO	World Health Organization
ZBI	Zarit Burden Interview

1 Introduction

This statistical analysis plan (SAP) covers the analyses of the LTE period and the analyses across both the placebo-controlled period and the LTE period of the study, 251AD201. A separate SAP has been prepared for the analyses of the placebo-controlled period.

Unless stated otherwise, all statistical tests will be 2-sided with statistical significance level of 0.05.

The statistical software, SAS[®] will be used for all summaries and analyses.

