3.5 Key Derived Variables

- Handling of missing items for scales
 - If any of the individual items for the primary efficacy endpoint and exploratory efficacy endpoints is missing, the total score of the corresponding endpoint will be imputed by prorating the observed scores [van Ginkel 2010].
 - For ADAS-Cog13, if 3 or fewer of 13 items (<25%) are missing, the total score will be imputed by the following algorithm: Total score = total score from the completed items * [maximum total score (=85) / maximum total score for the

CONFIDENTIAL

completed items]. The imputed number will be rounded up to the nearest integer. If more than 3 items are missing, the total score of ADAS-Cog 13 at that visit will be considered missing.

- For ADCS-ADL, if 8 or fewer of 32 items (<25%) are missing, the total score will be imputed by a similar algorithm as that for ADAS-Cog 13. The imputed number will be rounded down to the nearest integer. If more than 8 items are missing, the total score for ADCS-ADL at that visit will be considered missing.
- The same imputation algorithm will be applied to CDR-SB and MMSE, if only 1 box (of 6) of CDR is missing or if only 2 or fewer items (out of 11) are missing for MMSE. The imputed CDR-SB will be rounded up to the nearest half integer, and the imputed MMSE will be rounded down to the nearest integer. If the score from more than 1 box of CDR or more than 2 items of MMSE is not available, the CDR-SB or MMSE at that visit will be considered missing.
- The total score of the tertiary endpoint NPI-10 and FAQ will be imputed using the same prorating principle and round up to the nearest integer if only 1 item (out of 10) is missing.

- iADRS derivation

The iADRS is a composite score based on ADAS-Cog and ADCS-iADL (instrumental ADCS-ADL) [Wessels et al. 2015, Wessels et al. 2018]. The iADRS is calculated as a linear combination of total scores of the two individual components, the ADAS-Cog13 (score range 0 to 85) and the ADCS-iADL (score range 0 to 59). Because higher score on the ADAS-Cog13 reflect worse performance, whereas higher scores on the ADCS-iADL reflect better performance, the ADAS-Cog score is multiplied by (-1) in the calculation of the integrated scale. To anchor the ADAS-Cog at 0, a constant (85) is added. The iADRS score is then computed as the sum of the transformed ADAS-Cog13 and the ADCS-ADL, as shown in the formula below:

$$\text{iADRS score} = [(-1) (\text{ADAS-Cog13}) + 85] + \text{ADCS-iADL}$$

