The iADRS score ranges from 0 to 144 with lower scores indicating worse performance. If either ADAS-Cog13 or ADCS-iADL is missing, the iADRS score will be considered missing.

- EMACC derivation

The EMACC is a new and sensitive composite of well-known and validated neuropsychological tests that is suitable for examining the effect of disease modifying compounds on cognitive decline in the early Alzheimer Disease or MCI stage of Alzheimer's disease [Jaeger et al. 2018].

Cognitive variables (ISLT, DKEFS Category Fluency total correct score, DKEFS Letter Fluency, DSST, Trails A total time to complete) will be z-score transformed using the

CONFIDENTIAL

The information contained herein may not be used, disclosed, or published without the written consent of Biogen MA Inc.

baseline score’s mean and SD. The EMACC will be computed by taking the average of the z-scores across the five tests. If Trails A is missing, EMACC will be computed by taking the average of the z-scores across the remaining four tests. For the rest 4 component scores, if any of them is missing then the composite score will be missing.

- ADCOMS derivation

ADCOMS is a novel instrument developed to improve the sensitivity of currently available cognitive and functional measures for subjects in the prodromal stage of AD and mild AD dementia. It consists of 4 Alzheimer’s Disease Assessment Scale–cognitive subscale items, 2 Mini-Mental State Examination items, and all 6 Clinical Dementia Rating—Sum of Boxes items (Table 1). The composite score is a weighted linear combination of the individual scales items using the corresponding partial least squares (PLS) coefficients as weighting factors as listed in Table 1 [Wang et al. 2016]. If any of the individual item is missing, then the composite score will be missing. The range of ADCOMS is between 0 and 1.97.

Table 1. Items included in ADCOMS and their corresponding PLS coefficients

Scale	Item name	PLS coefficients
ADAS-cog	Delayed word recall	0.008
	Orientation	0.017
	Word recognition	0.004
	Word finding difficulty	0.016
MMSE	Orientation time	0.042
	Drawing	0.038
CDR-SB	Personal care	0.054
	Community affairs	0.109
	Home and hobbies	0.089
	Judgement and problem solving	0.069
	Memory	0.059
	Orientation	0.078

ADAS-cog, Alzheimer’s Disease Assessment Scale–cognitive subscale; CDR-SB, Clinical Dementia Rating, sum of boxes; MMSE, Mini-Mental State Exam; PLS, partial least squares.

	Statistical Analysis Plan Long-Term Extension Period	V1.0

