5.3 Efficacy Analysis

5.3.1 General Considerations

The analysis population for efficacy analysis is the same as the FAS and data from both the placebo-controlled and LTE periods will be include. All efficacy analyses will be presented by study treatment groups as defined in Section 3.3. The early start high-dose subjects are the subjects who were randomized to high-dose BIIB092 group in the PC period, and the late start high-dose subjects are the subjects who were randomized to Placebo in the PC period, regardless of enrollment of the LTE period or not.

The following comparison will be evaluated for the long-term efficacy of BIIB092:

- The early start high dose compared with the late start high dose.

The comparisons between low-dose and late start high dose, and middle-dose and late start high dose might be conducted. There will be no multiple comparison adjustments.

Visit windows for mapping efficacy endpoint

For efficacy data that are summarized by visit, assessment from all scheduled visits, EOS visit and unscheduled visits will be mapped to an appropriate analysis visit using a windowing scheme ([Appendix I](#)).

CONFIDENTIAL

The information contained herein may not be used, disclosed, or published without the written consent of Biogen MA Inc.

	Statistical Analysis Plan Long-Term Extension Period	V1.0
---	--	-------------

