5.3.4 Exploratory Efficacy Endpoints

The clinical endpoints assessing AD progression from Baseline include the results of the MMSE, ADAS-Cog13, ADCS-ADL, ISLT, eCog, FAQ, NPI-10, EMACC (composite score of ISLT, DKEFS, DSST, and Trails A), ADCOMS (composite score of selected items from CDR, MMSE, and ADAS-Cog 13) and iADRS.

The by visit summary and MMRM analysis will be performed for MMSE, ISLT, eCog, ADCS-ADL, FAQ, ADAS-Cog-13 (13-item), NPI-10, EMACC, ADCOMS, and iADRS as described in Section 5.3.2.1. For LTE interim analysis at PC DBL, all available records up to week 104 will be analyzed in MMRM table. The baseline and change from baseline scores at each post-baseline visit will be summarized by LTE treatment group at final analysis.

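### As written, the EMACC composite adds Trails A completion time with the wrong sign, so slowing on that test counts as improvement

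*SAP*

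**What the plan says.** The EMACC derivation in SAP section 3.5 has three steps.

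- **Standardise.** "Cognitive variables (ISLT, DKEFS Category Fluency total correct score, DKEFS Letter Fluency, DSST, Trails A total time to complete) will be z-score transformed" using the "baseline score’s mean and SD".
- **Average.** "The EMACC will be computed by taking the average of the z-scores across the five tests".
- **Missing data.** If only Trails A is missing, the other four z-scores are averaged. If any of those four is missing, EMACC is missing.

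The paragraph gives no sign for any component and does not say whether a high EMACC is good or bad. The iADRS derivation immediately before it does both. It explains that ADAS-Cog13 runs opposite to ADCS-iADL, states that "the ADAS-Cog score is multiplied by (-1) in the calculation of the integrated scale", and says which end of the scale is worse.

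SAP section 5.3.4 names the parts again, "EMACC (composite score of ISLT, DKEFS, DSST, and Trails A", and sends EMACC to the by-visit summaries and the MMRM of section 5.3.2.1. It adds nothing on direction.

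**The concern.** A composite is interpretable only if its parts point the same way. Here one part is elapsed time and the others are performance scores. A plain average lets worsening on Trails A cancel worsening on the other four tests.

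EMACC then goes through the same MMRM as the other exploratory scales, with LS mean differences, confidence intervals and p-values. If the text is programmed literally, those outputs describe a variable that is not overall cognition. Because the SAP states no direction, a reader of the results could not detect this from the plan.

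Consistency between documents also matters. SAP section 5.3.1 says that "data from both the placebo-controlled and LTE periods will be include", while the SAP introduction says that "A separate SAP has been prepared for the analyses of the placebo-controlled period". EMACC has to be one variable across both.

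**Working it through.** The documents give no figure for EMACC (no range, SD or expected change), so there is nothing of the plan's own to reproduce. The check applies the written rule directly.

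**Direction of each component**

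- Trails A is total time to complete, so a larger value is worse.
- Category Fluency is a total-correct score, so a larger value is better.
- ISLT: protocol section 8.1 defines impairment as a score below the normative mean, so a larger value is better.
- Letter Fluency and DSST: the documents do not state the direction. Higher is better under ordinary scoring, which is an assumption.

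The mixed direction is already established by Category Fluency and ISLT against Trails A.

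**Does any later step restore the sign?** No. A z-score divides by a positive SD, so it keeps direction. SAP section 3.4 defines change as post-baseline minus baseline, so the baseline mean cancels and the change in z is (post - baseline)/SD, with its sign unchanged. The MMRM in section 5.3.2.1 does not alter it.

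**What follows from the formula alone.** Each component has weight 1/5. If Trails A slows by 1 SD and nothing else changes:

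- as written: +1/5 = +0.2
- with reversal: -1/5 = -0.2

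**Mean change when the tests move together.** Let four tests worsen by d SD and Trails A by k·d.

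- As written: (-4d + kd)/5 = -(4 - k)d/5
- With reversal: (-4d - kd)/5 = -(4 + k)d/5
- Ratio: (4 - k)/(4 + k)

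| k | 0 | 0.5 | 1 | 1.5 | 2 |
|---|---|---|---|---|---|
| mean change as written / correct | 100% | 78% | 60% | 45% | 33% |

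**Standardised effect.** The wrong sign changes the variance as well as the mean. Assume equal SDs of change and a common correlation r between components, once all are aligned so that higher is better.

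- Variance as written: (5 + 4r)/25
- Variance with reversal: (5 + 20r)/25
- Ratio of standardised effects: [(4 - k)/(4 + k)] × √[(5 + 20r)/(5 + 4r)]

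At k = 1 this is 0.6 × √[(5 + 20r)/(5 + 4r)]:

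| r | 0 | 0.3 | 0.5 | 0.7 | 1 |
|---|---|---|---|---|---|
| ratio | 60% | 80% | 88% | 94% | 100% |

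For example, at r = 0.3: 0.6 × √(11/6.2) = 0.6 × 1.332 = 0.799. A simulation with these settings also gave 0.799.

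The ratio is not always below 1. At r = 0.3 it is 133% at k = 0, 104% at k = 0.5 and 44% at k = 2.

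If the SD of Trails A change is s times that of the others, the variances become (4 + s² + 12r ∓ 8rs)/25, with minus as written and plus with reversal. At k = 1 and r = 0.3 the ratio is then:

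- s = 0.5: 0.6 × √(9.05/6.65) = 70%
- s = 2: 0.6 × √(16.4/6.8) = 93%

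**Interaction with the missing-data rule.** Take a uniform decline of d SD.

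- Trails A present, as written: (-4d + d)/5 = -0.6d
- Trails A missing: -4d/4 = -d
- Trails A present, with reversal: -5d/5 = -d

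As written, the same decline scores differently depending on whether Trails A was completed. With the sign fixed, both values are -d.

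**The case against.** The strongest reply is that this is an incomplete description, not a wrong analysis. The placebo-controlled SAP, the derivation programs and the source cited for EMACC were not available. Any of them may fix the orientation of Trails A, and an experienced programmer might reverse it without being told. That limit stands: nothing here shows that the computed score is wrong. It does not rescue the text. Where this SAP relies on the placebo-controlled SAP it says so, as for infusion reactions, laboratory criteria and antibody definitions; the EMACC paragraph makes no such reference. The iADRS derivation also cites published sources, yet spells out its reversal.

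A second reply is that little depends on it. EMACC is not listed among the LTE endpoints in SAP section 2.2 and is exploratory in section 5.3.4, and section 5.3.1 makes no multiplicity adjustment. In addition, the first LTE visit for the five component tests is Week 108 (protocol Table 2; SAP Appendix I, Table 1), while the interim MMRM uses records only up to Week 104. Read plainly, EMACC at the interim therefore contains only placebo-controlled data, and LTE-period scores enter at the final analysis. All of this stands and limits the weight of the point.

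Third, the sizes beyond 0.2 per SD rest on assumed values of k, r and s. That is correct, and the assumed grid runs from 44% to 133%, so even the direction of the effect on a standardised difference is not determined by the documents. The sign fault does not depend on those assumptions.

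**Conclusion.** The concern holds for the text as written. The formula gives Trails A time the same positive weight as tests scored in the opposite direction, and nothing in the supplied documents corrects it. The certain consequence is a movement of +0.2 instead of -0.2 in EMACC per SD of slowing. If Trails A worsens along with the other tests, the mean decline is understated: 60% of the correct value when all five worsen equally, under the ordinary scoring direction for Letter Fluency and DSST. The size of any distortion in the early-start versus late-start comparison is unknown.

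This should be fixed, but its reach is limited to one exploratory endpoint. Confidence is high that the rule as stated is wrong; no claim is made about the programmed score.

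**What to change.** In SAP section 3.5, state that the Trails A z-score is multiplied by -1 before averaging and that higher EMACC means better performance. Before finalising, confirm that the placebo-controlled SAP and the derivation programs use the same rule; if they differ, align them so that EMACC is the same variable in both periods.

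The cost is one sentence and one check of the other SAP and the code. If the code already reverses Trails A, the sentence only brings the SAP into line with it.

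As a related query, not an established error: while section 3.5 is open, state whether the two MMSE items in ADCOMS enter as points lost, since their weights in that section's Table 1 are positive, like those of the ADAS-Cog and CDR items.

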3.4 Dates and Points of Reference

The study day and baseline are defined for each analyses period respectively

1. LTE period

- Study Day 1: the date of the first dose of study treatment in the LTE period
- Study Day
 - For a date on or after Study Day 1

$$\text{Study Day} = (\text{Date of Interest}) - (\text{Study Day 1}) + 1$$
 - For a date before Study Day 1

$$\text{Study Day} = (\text{Date of Interest}) - (\text{Study Day 1})$$
- LTE baseline: the baseline value for the LTE period is defined as the most recent non-missing measurement collected prior to the first dose in the LTE period.
- Change from baseline will be defined as post-baseline value minus baseline value

2. Placebo-controlled and LTE period

- Study Day 1: the date of the first dose of study treatment in the PC period

CONFIDENTIAL

The information contained herein may not be used, disclosed, or published without the written consent of Biogen MA Inc.

- Study Day
 - For a date on or after Study Day 1
Study Day = (Date of Interest) – (Study Day 1) + 1
 - For a date before Study Day 1
Study Day = (Date of Interest) – (Study Day 1)
- PC and LTE baseline: the baseline value for the Placebo-controlled and LTE period is defined as the most recent non-missing measurement collected prior to the first dose in the PC period.
- Change from baseline will be defined as post-baseline value minus baseline value

3. Placebo-controlled and LTE active treatment period

- Study Day 1: the date of the first dose of BIIB092. For low-dose, medium-dose and early start high-dose subjects, this will be the date of first dose of BIIB092 in the placebo-controlled (PC) period; for late start high-dose subjects, this will be the date of first dose of BIIB092 in the LTE period.
- Study Day
 - For a date on or after Study Day 1
Study Day = (Date of Interest) – (Study Day 1) + 1
 - For a date before Study Day 1
Study Day = (Date of Interest) – (Study Day 1)
- Active treatment baseline: the baseline value for the active treatment period and is defined as the most recent non-missing measurement collected prior to study day 1.
- Change from baseline will be defined as post-baseline value minus baseline value

For data that are summarized by visit, assessment from all scheduled visits, EOS visit and unscheduled visits will be mapped to an appropriate analysis visit using a windowing scheme as describe in [Appendix I](#)

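### When Trails A is missing at a visit, EMACC change compares a four-test score with a five-test baseline, which adds a spurious shift to that record; any effect on group contrasts is conditional and small

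*SAP*

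**What the plan says.** SAP section 3.5 gives three rules for EMACC.

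- All tests present: "The EMACC will be computed by taking the average of the z-scores across the five tests".
- Trails A missing: "If Trails A is missing, EMACC will be computed by taking the average of the z-scores across the remaining four tests".
- Any other test missing: "For the rest 4 component scores, if any of them is missing then the composite score will be missing".

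Each test is standardised with the "baseline score’s mean and SD". Trails A enters as "Trails A total time to complete", and no reversal of sign is stated.

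Section 3.4 fixes the comparison point for efficacy: "the baseline value for the Placebo-controlled and LTE period is defined as the most recent non-missing measurement collected prior to the first dose" in the placebo-controlled period. It then states: "Change from baseline will be defined as post-baseline value minus baseline value". Neither section says that the two values must be built from the same tests.

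Section 5.3.4 lists EMACC among ten exploratory endpoints for by-visit summary and MMRM, and adds: "The baseline and change from baseline scores at each post-baseline visit will be summarized by LTE treatment group at final analysis". The MMRM in section 5.3.2.1 models change from baseline, with baseline and baseline-by-visit among the fixed effects.

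**The concern.** A four-test mean and a five-test mean are different scores. Subtracting one from the other gives a non-zero change even when no test result has moved, unless the participant's Trails A z-score happens to equal the mean of the other four. Only the Trails A exception allows this. In the same section, ADCOMS is set to missing if any item is missing, iADRS if either component score is missing, and EMACC itself if any of the other four tests is missing.

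At stake are the accuracy of individual change scores, some added noise in the by-visit summaries and, if Trails A goes missing differently across groups, a shift in the comparison of early-start with late-start high dose. Nothing in the supplied documents rebuilds the baseline on four tests, and no sensitivity analysis addresses the point.

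**Working it through.** The documents give no SD, effect size or power for EMACC, so there is no planned figure to reproduce. The rules come from SAP 3.4 and 3.5. The z-scores, correlations and missingness rates below are assumptions.

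**Artefact for one record.** Let M4 be the baseline mean z of the four other tests and zT the baseline Trails A z. Trails A is missing at the visit and no other score has changed.

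- Baseline EMACC = (4 × M4 + zT)/5
- Visit EMACC = M4
- Recorded change = M4 - (4 × M4 + zT)/5 = (M4 - zT)/5

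| M4 | zT | Baseline | Visit | Recorded change |
|---|---|---|---|---|
| 0 | -1 | -0.20 | 0 | +0.20 |
| 0 | -2 | -0.40 | 0 | +0.40 |
| 0 | +2 | +0.40 | 0 | -0.40 |
| -0.5 | -2 | -0.80 | -0.50 | +0.30 |
| -0.5 | -0.5 | -0.50 | -0.50 | 0 |

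If Trails A is missing only at baseline, the sign reverses. With M4 = 0 and zT = -1.5, an unchanged participant is recorded at -0.30 - 0 = -0.30.

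**With real change.** The term is additive: recorded change = [M4(visit) - M4(baseline)] + (M4 - zT)/5. Take M4 = 0 and zT = -1.5, with every test falling by 0.25. Baseline is -0.30 and the four-test visit score is -0.25, so the recorded change is +0.05. On matched tests it is -0.25, the true change.

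**Spread and average across participants.** Assume equal correlation r between tests and Trails A reversed so that higher is better. The artefact then has SD √((1 - r)/20): 0.22, 0.19, 0.16 and 0.12 for r = 0, 0.3, 0.5 and 0.7. All z-scores are centred at baseline, so its mean is zero when missingness is unrelated to the Trails A profile.

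**If the slowest 10% at baseline are those missing.** Their mean zT is about -1.755, and the mean artefact is (1 - r) × 1.755/5: +0.35, +0.25, +0.18 and +0.11 for the same four r. If raw time is used unreversed it is -(1 + r) × 1.755/5: -0.35, -0.46, -0.53 and -0.60. The undocumented sign therefore decides the direction.

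**Group contrast.** Suppose the slowest 5% are missing in one group and the slowest 15% in the other, signs aligned. Each group mean shifts by (1 - r)/5 × φ(q), where φ is the standard normal density at the cut-off: 0.1031 for 5% and 0.2332 for 15%. The difference is (1 - r)/5 × 0.130, which gives 0.026, 0.018, 0.013 and 0.008 for r = 0, 0.3, 0.5 and 0.7. A single-visit ANCOVA simulation at r = 0.3 and 0.5 gave about the same bias (0.013 to 0.018), and matched components removed it. With a flat artefact of 0.30 per affected record, the shift is (0.15 - 0.05) × 0.30 = 0.03. Equal missingness with equal profiles cancels.

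**The case against.** The strongest counter-argument concerns the MMRM. With baseline and baseline-by-visit in the model, analysing change or analysing the visit score gives the same treatment contrast, so subtracting a five-test baseline does not in itself drive the group comparison. That is correct, and it means the subtraction acts directly on the descriptive change summaries. It does not clear the model, however. The visit score is still a four-test mean for some participants and a five-test mean for others, and the baseline covariate does not absorb the difference when missingness differs by group. The missing-at-random assumption in section 5.3.2.1 does not help either, because the four-test score enters as an observed value.

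A reader might infer that participants who decline until they cannot finish Trails A receive an artificial gain, so that the rule hides decline. The documents do not support this.

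- The artefact uses baseline values only. If all five tests start at 0, the other four stay at 0 and Trails A is then lost, the artefact is zero.
- If the unobserved Trails A score in that case would have been -2, the five-test change would be -0.40. The SAP rule and a matched four-test rule both record 0. That loss comes from informative missingness, not from the change in composition.
- No passage says that failure to finish is recorded as missing, and no missingness rate is given.
- Without a stated sign for completion time, neither gain nor loss can be asserted.

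It can also be said that averaging the available tests is a form of prorating, which section 3.5 uses elsewhere, and that the cited EMACC source may define the exception. That may justify the four-test score at a visit. It does not justify comparing it with a five-test baseline. The placebo-controlled SAP was not available, but this SAP gives its own EMACC derivation without deferring to it.

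**Conclusion.** The point holds as a derivation error in individual change scores. For anyone with Trails A at baseline but not at a visit, the plan as written adds (M4 - zT)/5 to the recorded change. That is 0.20 to 0.40 z-units in size when baseline Trails A differs from the other tests by 1 to 2 SD. The formula follows from SAP 3.4 and 3.5 alone and applies whichever way Trails A is signed; the direction remains open.

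Group-level bias is conditional. It requires missingness, or the baseline profile of those missing, to differ between groups, and it is then roughly 0.01 to 0.03 z under the assumed 5% versus 15%. A claim that the rule is known to distort the early-start versus late-start comparison would go beyond the documents. EMACC is exploratory, and neither CDR-SB nor the primary safety endpoint is affected. This is a worthwhile clarification, not a threat to the trial's main conclusions.

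**What to change.** In SAP 3.5, state that change in EMACC uses the same tests at both times:

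- Trails A missing at a post-baseline visit: compute that visit's change from the four-test baseline.
- Trails A missing at baseline: use the four-test version throughout for that participant.

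In SAP 5.3.2.1, state which baseline EMACC is the MMRM covariate. One option is a single fixed value per participant: five-test, or four-test if Trails A is missing at baseline. Section 3.4 should acknowledge the visit-specific baseline. It would also help to state the sign of the Trails A z-score and to report Trails A missingness by group and visit, with a sensitivity analysis restricted to records with all five tests.

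The cost is a few SAP sentences, a small derivation change and a visit-specific baseline for the affected records. No new data are needed and no visits are lost. The change removes the composition artefact; it does not recover decline that goes unobserved because a participant could not finish Trails A.

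### ADCOMS as written weights two higher-is-better MMSE items positively alongside higher-is-worse items, with no reversal and no stated score direction

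*SAP*

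**What the plan says.** The ADCOMS derivation is in SAP 3.5 (Key Derived Variables). On content: "It consists of 4 Alzheimer’s Disease Assessment Scale–cognitive subscale items, 2 Mini-Mental State Examination items", plus all six CDR boxes. On scoring: "The composite score is a weighted linear combination of the individual scales items using the corresponding partial least squares (PLS) coefficients as weighting factors". The coefficient table in that section lists 12 weights, none negative. The MMSE rows read "Orientation time 0.042" and "Drawing 0.038"; the largest weight is a CDR box, "Community affairs 0.109". One further figure is given: "The range of ADCOMS is between 0 and 1.97". The paragraph does not say whether the MMSE items enter as points correct or as errors, or whether a higher ADCOMS is better or worse.

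The same section shows which way the component scales run:

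- **ADAS-Cog 13:** stated to be worse when higher. For iADRS, "the ADAS-Cog score is multiplied by (-1) in the calculation of the integrated scale", a constant of 85 is added, and the direction of the composite is given.
- **Prorated totals:** ADAS-Cog 13 and CDR-SB are rounded up. ADCS-ADL is rounded down, and "the imputed MMSE will be rounded down to the nearest integer".

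SAP 5.3.4 (Exploratory Efficacy Endpoints) gives ADCOMS a by-visit summary and an MMRM, with records up to Week 104 used at the interim.

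**The concern.** A weighted sum works as a severity score only if every item points the same way once weighted. Ten of the twelve items (four ADAS-Cog, six CDR) rise with impairment. The two MMSE items, taken as recorded, fall with impairment, yet carry the same sign. A programmer who follows the text would produce a score in which MMSE decline offsets decline elsewhere, and a participant who worsens on both an MMSE item and a CDR box can be scored as improved.

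The by-visit summary and MMRM for ADCOMS would inherit this. Because no direction is stated, a reader of the output also could not tell from the SAP which sign of a treatment difference favours BIIB092.

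**Working it through.** **Inputs from SAP 3.5.** The weights are:

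- ADAS-Cog: delayed recall 0.008, orientation 0.017, word recognition 0.004, word finding 0.016
- MMSE: time 0.042, drawing 0.038
- CDR boxes: 0.054, 0.109, 0.089, 0.069, 0.059, 0.078 (sum 0.458)

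**Direction.** The SAP never states the MMSE direction outright, so it is inferred. The rounding rules move prorated scores towards impairment: up for ADAS-Cog 13 (stated higher-is-worse), down for ADCS-ADL (SAP 3.5 states that its instrumental part, ADCS-iADL, is higher-is-better). CDR-SB goes up with ADAS-Cog 13; MMSE goes down with ADCS-ADL. Protocol 8.1 is consistent with this: this early-stage population enters with MMSE 22 to 30, and the permitted CDR global score is 0.5 for MCI and 0.5 or 1 for mild AD.

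**Assumption.** Item maxima are not in the documents. Standard values are assumed: ADAS-Cog 10, 8, 12, 5; MMSE 5 and 1; CDR 3 per box.

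**Reproducing the stated range.**

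- ADAS-Cog: 10×0.008 + 8×0.017 + 12×0.004 + 5×0.016 = 0.344
- MMSE: 5×0.042 + 1×0.038 = 0.248
- CDR: 3×0.458 = 1.374
- Total: 0.344 + 0.248 + 1.374 = 1.966, which rounds to the stated 1.97

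**What the ends of the range mean under each coding.**

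| MMSE coding | Arithmetic range | Unimpaired record | Maximally impaired record |
|---|---|---|---|
| Points as recorded, positive weight | 0 to 1.966 | 0.248 | 0.344 + 1.374 = 1.718 |
| Maximum minus points, positive weight | 0 to 1.966 | 0 | 1.966 |
| Points as recorded, negative weight | −0.248 to 1.718 | −0.248 | 1.718 |

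The first two codings give the same arithmetic range; only negative weights are ruled out. With points as recorded, the span from unimpaired to maximally impaired is 1.718 − 0.248 = 1.470, against 1.966 with reversal, a loss of about 25%. The MMSE items carry 0.248/1.966 = 12.6% of the range.

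**Sensitivity to the assumed maxima.** If the MMSE maxima were 4 to 6 for time and 1 to 2 for drawing, an unimpaired record scored on recorded points would lie between 4×0.042 + 1×0.038 = 0.206 and 6×0.042 + 2×0.038 = 0.328. It is never 0. The per-point signs below do not depend on any maximum.

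**Per-point effect.** One time-orientation point lost moves ADCOMS by −0.042 on recorded points and +0.042 on reversed points, a gap of 0.084. A lost drawing point gives −0.038 against +0.038.

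**Two worked changes.**

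- One time point lost and CDR Orientation worse by 0.5: as recorded, −0.042 + 0.5×0.078 = −0.003; reversed, 0.042 + 0.039 = +0.081.
- One time point lost and CDR Memory worse by 0.5: as recorded, −0.042 + 0.5×0.059 = −0.0125; reversed, 0.042 + 0.0295 = +0.0715.

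Not every pair flips sign. A half-point worsening in Community affairs adds 0.5×0.109 = 0.0545, which exceeds 0.042.

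**Change from baseline and treatment difference.** Let A be the weighted ADAS-Cog and CDR part and M the weighted MMSE points as recorded. The change is ΔA + ΔM as written and ΔA − ΔM with reversal. When M falls, the written score understates the change by twice the weighted MMSE loss. The between-arm difference follows the same form: δA + δM as written, δA − δM with reversal. It is attenuated only if the arm that does better on A also does better on the MMSE items.

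**The case against.** The strongest reply is that this is an omission and not a wrong formula. The SAP does not say that MMSE items enter as points correct, it cites the instrument's source publication beside the coefficients, and a separate SAP covers the placebo-controlled period. Either may give the item coding, and neither is available here. That stands to this extent: the documents cannot show how ADCOMS is programmed, and reversal may well have been intended. It does not remove the conflict. The sentence is an operative rule, and its natural reading gives the wrong sign. The ADCOMS paragraph does not refer to the placebo-controlled SAP, although other parts of this SAP do so when they rely on it. For iADRS, the neighbouring composite, the reversal is written out.

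A reader might infer that the stated range proves error scoring. It does not: recorded and reversed MMSE points both span 0 to 1.966. The range supports reversal only if its ends are meant as unimpaired and maximally impaired, which the SAP does not say.

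A reader might also infer that any treatment difference in ADCOMS would shrink. That is too strong. If the arms do not differ on the two MMSE items, the difference is unchanged; if they differ in the opposite direction to the other items, it grows.

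The stakes are also modest. ADCOMS is exploratory, is not among the endpoints in Protocol 6 or SAP 2.2, and plays no part in multiplicity control. CDR-SB, MMSE and ADAS-Cog 13 are each analysed separately.

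**Conclusion.** Wrong as written. Applied literally to recorded MMSE points, the rule gives the two MMSE items the opposite direction to the other ten: −0.042 per lost time-orientation point and −0.038 for drawing, where the same amounts should be added. This rests on the MMSE being higher-is-better, which is inferred from the SAP's rounding rules and is consistent with the entry criteria. The figures 0.248, 1.718 and the 25% loss of span rest in addition on the assumed item maxima, which reproduce the stated 1.97.

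If the text is followed, change from baseline is understated whenever the MMSE items decline with the others, and a treatment difference is attenuated when the arms differ on the MMSE items in the same direction as on the rest. No trial-level attenuation can be estimated from the documents. Nor do they support saying that reported ADCOMS results will be wrong, since the code may already reverse the items. The consequence is limited to this exploratory endpoint; CDR-SB is unaffected. It should be corrected before ADCOMS is analysed.

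**What to change.** In SAP 3.5, add that the two MMSE items enter ADCOMS as item maximum minus points scored, before weighting; that higher ADCOMS is worse; and that 0 is best and 1.97 worst. State the item maxima used. The coefficients and the stated range need not change.

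In programming, check that an all-unimpaired record returns 0 and that losing one time-orientation point, with everything else fixed, raises the score by 0.042.

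The cost is a sentence or two in the SAP and, if the code does not already reverse the items, one line of derivation. No new data are needed.
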